The likelihood ratio of a positive and a negative result for ultrasonography were 10.74 and 0.03 respectively, and that for capnography were infinity and 0.04 respectively.

The kappa value was 0.749 (95% CI: 0.567 – 0.931) which meant a good degree of agreement of result between these two methods.

The average time taken for confirmation of endotracheal tube by ultrasonography and capnography were 26.79 ± 7.64 seconds and 43.03 ± 8.71 seconds (mean \pm standard deviation) respectively. The median time for confirmation was 26 seconds with interquartile range [15 - 37] seconds for ultrasonography and 42 seconds with interquartile range [29 - 55] seconds for capnography. Ultrasonography was found to be faster than capnography by 16.36 ± 3.23 seconds (mean \pm standard deviation) and the difference in time was significant ($p = 0.011$).

Conclusion:

Ultrasonography and waveform capnography are both reliable and accurate methods of confirming endotracheal tube position. The use of ultrasound with capnography will help reduce time and increase precision of confirming endotracheal tube position. Ultrasound can confirm endotracheal tube position before manual bag ventilations, and thus may prevent aspiration of gastric contents into patient's lungs.

Keywords: Endotracheal intubation; ultrasonography; capnography.

TABLE OF CONTENTS

Serial No.	Contents	Page No.
1	Introduction	7
2	Literature Review	19
3	Objectives	30
4	Hypothesis	31
5	Methodology	32
6	Results	45
7	Discussion	55
8	Limitations	68
9	Conclusion	69
10	Recommendations	70
11	References	71
12	Appendices	
	Appendix A - PAC Form	77
	Appendix B - Consent	79
	Appendix B – Proforma	80
	Appendix D – Thesis approval letter from IRB	82

LIST OF ABBREVIATIONS

%	Percentage
>	Greater than
<	Lesser than
±	Plus– Minus
α	Alpha
ACLS	Advanced Cardiac Life Support
AHA	American Heart Association
ASA	American Society of Anesthesiologists
β	Beta
BMI	Body Mass Index
BPM	Beats Per Minute
CI	Confidence Interval
CL	Cormack Lange
CO ₂	Carbon Dioxide
COPD	Chronic Obstructive Pulmonary Disease
CPR	Cardiopulmonary Resuscitation
DLT	Double-Lumen Tube
ECG	Electrocardiogram
Eg	Example
ET	Endotracheal
ETCO ₂	End Tidal CO ₂
NIBP	Non-Invasive Blood Pressure
IRB	Institutional Review Board

IOM	Institute of Medicine
IQR	Interquartile Range
κ	Kappa value
Kg	kilogram
LMA	Laryngeal Mask Airway
LR ⁺	Likelihood ratio of a positive test
LR ⁻	Likelihood ratio of a negative test
MCVTC	Manmohan Cardiothoracic Vascular and Transplant Center

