Chintamani et al³⁴ did a prospective, observational study was on 100 patients requiring tracheal intubation for general anaesthesia and used both capnography and transverse, suprasternal transtracheal static ultrasound after intubation to confirm the endotracheal tube placement. Ultrasound detected all five cases of oesophageal intubation, but could not detect five patients with correct tracheal intubation. Ultrasonography had a sensitivity of 96.84% (95% confidence interval [CI]: 94.25% - 96.84%), specificity of 100% (95% CI: 50.6% – 100%), positive predictive value of 100% (95% CI: 97.3% – 100%) and negative predictive value of 62.5% (95% CI: 31.6% – 62.5%) when compared to capnography as the standard method for endotracheal tube confirmation. Kappa value was found to be 0.76, indicating a good agreement between ultrasonography and capnography for confirmation of endotracheal tube placement. Time taken for confirmation of endotracheal tube was 8.989 ± 1.043 sec by capnography versus 12.0 ± 1.318 sec by ultrasound ($p < 0.001$).

OBJECTIVES

General:

To compare ultrasonography imaging and waveform capnography for endotracheal intubation confirmation in a tertiary hospital operating room setting.

Specific:

1. To determine the time taken by real-time ultrasonography imaging in detecting endotracheal tube placement.
2. To determine the time taken by capnography waves in detecting endotracheal tube placement.
3. To calculate the sensitivity and specificity of capnography and ultrasonography in detecting endotracheal tube placement.
4. To calculate positive and negative predictive values of these two methods in detecting endotracheal tube placement.
5. To interpret the degree of agreement of result obtained with ultrasonography and capnography using kappa statistics.

HYPOTHESIS

Transtacheal ultrasonography and waveform capnography are both accurate methods of verifying endotracheal tube placement after intubation.

Real-time transtacheal ultrasound is a faster method of detecting endotracheal tube placement compared to waveform capnography.

METHODOLOGY

Study design

Research Method: Qualitative and quantitative.

Type of study: Prospective, observational.

Study Population: Patients admitted for elective surgery at Tribhuvan University Teaching Hospital (TUTH) and Manmohan Cardiothoracic Vascular and Transplant Center (MCVTC) under general anaesthesia.

Study site: Operating rooms, TUTH and MCVTC.

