Duration of study: 6 months. The study was conducted at MCVTC from January 17, 2017 to April 14, 2017. It was continued at TUTH from April 15, 2017 to July 14, 2017.

Sampling Method: Non-probability sampling.

Sample size: Total 95 patients were taken for analysis.

The formula for sample size with $(1 - \alpha)\%$ confidence level and with maximum margin error of estimate of “d” for constructing confidence interval of true value of sensitivity or specificity using normal approximation is given as follows³⁵:

$$n = \frac{Z_{\frac{\alpha}{2}}^2 \hat{P}(1 - \hat{P})}{d^2}$$

Where \hat{P} is pre-determined value of sensitivity or specificity that is ascertained by previous published data or clinician experience or judgment.³⁵

For $\alpha = 0.05$, $Z_{\alpha/2}$ is inserted by 1.96.^{35,36}

Excerpted from the meta-analysis done by Chou et al⁶ where they found the sensitivity and specificity of suprasternal transtracheal ultrasound for endotracheal tube confirmation to be 0.98 and 0.94 respectively, the specificity value for \hat{P} in the equation was taken. Hence setting margin of error “d” at 5%, we could equate to:

$$n = 1.96^2 \times 0.94 \times 0.06 / 0.05^2 = 86.66$$

Adjusting for 10% drop outs and defaulters, a sample size of 95 was thus taken.

Inclusion criteria:

ASA I and II patients of both sexes above 16 years of age undergoing general anaesthesia with endotracheal tube placement.

Exclusion criteria:

- Patient refusal
- ASA physical status III and above
- History of prior difficult bag and mask ventilation or difficult intubation
- History of prior oro-nasal or neck injuries, burns or scars
- Active oral, pharyngeal or tracheal infection or inflammatory changes
- Anticipated difficult airway or difficult intubation during preanaesthetic examination, with Mallampati grades II and above
- Lung parenchymal and pleural diseases. Examples: asthma, COPD, bronchiectasis, reactive lung diseases, pneumonia, tuberculosis, pleural effusion, pneumothorax, lung or pleural malignancy etc.
- Emergency surgery

- Patients with known oesophageal pathology. Examples: oesophageal carcinoma, stricture, tracheoesophageal fistula etc.
- Full stomach or patients at risk of aspiration, e.g. pregnancy
- Patients with a nasogastric tube in situ
- NYHA grade 2 and above

Materials and Methods

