Both ultrasonography and waveform capnography were found to be good, reliable and fairly accurate diagnostic methods of confirming endotracheal tube position. Ultrasonography was comparable diagnostically with capnography for endotracheal tube confirmation. The comparisons of the pretest and posttest probabilities of the two methods are shown in table 10.

Table 10. Comparison of the diagnostic characteristics of ultrasonography and waveform capnography.

	Ultrasonography	Waveform Capnography
Sensitivity in % (95% CI)	97.62 (91.66- 99.71)	96.43 (89.92 - 99.26)
Specificity in % (95% CI)	90.91 (58.72 - 99.77)	100 (71.51 - 100)
PPV in % (95% CI)	98.80 (92.67- 99.81)	100 (100 – 100)
NPV in % (95% CI)	83.33 (55.66 - 95.22)	78.57 (54.69 - 91.76)
Accuracy in % (95% CI)	96.84 (92.92 - 100)	96.84 (92.92 - 100)
Positive likelihood ratio	10.74	Infinity
Negative likelihood ratio	0.03	0.04

(CI= Confidence Interval, PPV= Positive Predictive Value, NPV= Negative Predictive Value)

Both ultrasonography and capnography together had correctly identified 10 out of the 11 oesophageal intubations. The 84 tracheal intubations were correctly identified by both ultrasonography and capnography or either one of these methods. Using the same formula (page 35), the combined accuracy of both the methods together was 98.94% (94 divided by 95, in percentage).

The analysis of agreement between the ultrasonography and capnography results was done using Cohen's kappa statistics. A kappa value of 0.749 with 95% confidence interval of (0.567 – 0.931) and standard error of 0.093 was found. The kappa value therefore showed a good agreement between the result of these two methods.

Time taken for endotracheal tube confirmation

Real-time ultrasonography was faster than waveform capnography for endotracheal tube confirmation in all cases. The mean time for confirmation by ultrasonography was 26.79 ± 7.64 seconds (mean \pm standard deviation). The mean time for confirmation by capnography was 43.03 ± 8.71 seconds.

The mean difference in time was 16.36 seconds (95% CI: 15.70sec – 17.02 sec). The median difference in time was 16 seconds. The standard deviation in difference in time was 3.23 seconds. The standard error of mean (SEM) was 0.332 seconds. The difference in time was highly significant ($p = 0.011$).

Table 11. Time taken for endotracheal tube confirmation.

	Range (in seconds)	Mean \pm SD (in seconds)	Median (in seconds)	IQR (in seconds)	p-value

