Time taken by ultrasonography	14 - 50	26.79 ± 7.64	26.00	[15 - 37]	
Time taken by capnography	27 - 67	43.03 ± 8.71	42.00	[29 - 55]	
Difference in time (ultrasonography - capnography)	9 - 24	16.36 ± 3.23	16.00		0.011

(SD = Standard Deviation, IQR = Inter-Quartile Range, Range = Maximum-minimum values)

A subgroup analysis was done to test whether the time delay in sidestream capnograph could have affected the p-value obtained in difference in time. Two subgroups were divided: one subgroup in which sidestream capnography was used, and the other subgroup in which mainstream capnography was used. There were 37 patients in the mainstream subgroup and 58 patients in the sidestream subgroup. The median time for confirmation of endotracheal tube position in mainstream subgroup was 37 seconds. The median time for confirmation of endotracheal tube position for

capnography in sidestream subgroup was 45.5 seconds. The findings of difference in time between ultrasonography and capnography methods in these subgroups are summarized in table 12.

Table 12. Subgroup analysis for difference in time taken for endotracheal tube confirmation.

Difference in time (ultrasonography-capnography)	Range (in seconds)	Mean \pm SD (in seconds)	Median (in seconds)	p-value
Mainstream subgroup (n=37)	9 - 19	14 \pm 2.62	14	p < 0.01
Sidestream subgroup (n=58)	12 - 24	17.87 \pm 2.64	17.50	p < 0.01

(SD = Standard Deviation, Range = Maximum - minimum values)

The distribution was found to be normal in both subgroups on applying Shapiro-Wilk test (p < 0.01). Student's t- test was used to determine the p-value of difference in time to confirm endotracheal tube position between the two subgroups. The p-value, p < 0.01 was obtained in both the subgroups, which meant that use of sidestream capnography with a delay time did not affect the significant difference in time between ultrasonography and capnography found in this study.

DISCUSSION

Both ultrasonography and waveform capnography were found to be reliable and accurate methods of confirming endotracheal tube position in this study. The variables that were studied and analyzed in this study are now discussed further.

Descriptive data

The results of this study were not affected by the demographic and physical health profiles of the subjects.

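### Both methods are concluded to be accurate without qualification, but recognition of oesophageal tubes rests on 11 tubes and is too imprecise to support that

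*Combined protocol and SAP*

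**What the plan says.** The Hypothesis section states first that the two methods "are both accurate methods of verifying endotracheal tube placement after intubation", and second that ultrasound is faster. Neither that section nor Methodology gives a minimum sensitivity, specificity or overall accuracy that would count as accurate.

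The surrounding plan is written as estimation. Specific objectives 3 and 4 are to calculate sensitivity, specificity and predictive values. The Sample size section uses a confidence-interval formula at alpha 0.05, where Z "is inserted by 1.96". It takes sensitivity and specificity of "suprasternal transtracheal ultrasound for endotracheal tube confirmation to be 0.98 and 0.94 respectively", says that "the specificity value for \hat{P} in the equation was taken", and sets the margin of error "at 5%, we could equate to" n = 86.66, raised to 95 for drop-out.

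Table 10 prints the intervals for ultrasonography and then capnography: "Specificity in % (95% CI) 90.91 (58.72 - 99.77) 100 (71.51 - 100)".

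The Abstract concludes: "Ultrasonography and waveform capnography are both reliable and accurate methods of confirming endotracheal tube position". The Discussion opens: "Both ultrasonography and waveform capnography were found to be reliable and accurate methods of confirming endotracheal tube position in this study". The Conclusion section goes further and calls the two methods equal in these respects. Limitations covers the mix of capnograph types and the ultrasound operators, but not the number of oesophageal tubes or the width of the specificity intervals.

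**The concern.** A hypothesis with no criterion cannot fail, so reporting its wording back as a finding adds nothing to the estimates. Here the wording also merges two different abilities. Sensitivity in this study is recognition of a tube in the trachea and has 84 tubes behind it. Specificity is recognition of a tube in the oesophagus and has 11.

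Missing an oesophageal tube is the error that confirmation exists to catch, and the Recommendations rely on catching it when they speak of preventing aspiration in cases of oesophageal intubation. A reader of the Abstract or Conclusion alone would take that ability as shown to the same standard as the other.

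**Working it through.** **Inputs.** Planning specificity 0.94, margin 0.05 and Z = 1.96 (Sample size). Ultrasound: TP 82, FN 2, TN 10, FP 1 (Table 8). Capnography: TP 81, FN 3, TN 11, FP 0 (Table 9). The stated interval method is Clopper-Pearson (Methodology, beside Table 1).

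**1. Reproduce the planned size.** n = Z² × P × (1 − P) / d² = 1.96² × 0.94 × 0.06 / 0.05² = 86.66, as printed. 86.66 × 1.1 = 95.3, the stated 95.

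**2. Reproduce the printed intervals (exact, two-sided 95%).**

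| Quantity | Count | Estimate | Exact 95% CI |
|---|---|---|---|
| Ultrasound sensitivity | 82/84 | 97.62% | 91.66% to 99.71% |
| Capnography sensitivity | 81/84 | 96.43% | 89.92% to 99.26% |
| Ultrasound specificity | 10/11 | 90.91% | 58.72% to 99.77% |
| Capnography specificity | 11/11 | 100% | 71.51% to 100% |

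All four agree with Table 10.

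**3. Best result that 11 tubes allow.** With no errors, the exact lower limit is 0.025^(1/11) = 0.715. Other intervals for 11/11 have lower limits of 74.1% (Wilson), 76.2% (one-sided 95% exact) and 80.0% (Jeffreys). The Wald formula also printed in Methodology gives 11/11 an interval of zero width at 100%, which is an artefact of that formula.

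**4. Planned against achieved precision.** The denominator of specificity is oesophageal tubes, so a half-width of 0.05 at P = 0.94 needs about 87 of them. With 11, the half-width by the same formula is 1.96 × √(0.94 × 0.06 / 11) = 0.140, or ±14 points, nearly three times the planned ±5.

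**5. How easily a weaker method could give these counts.** Suppose, as an illustration, a true specificity of 80%, one oesophageal tube in five missed.
- P(11/11) = 0.8^11 = 0.086.
- P(at least 10/11) = 0.8^11 + 11 × 0.8^10 × 0.2 = 0.086 + 0.236 = 0.322.

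Ultrasound's count or better would therefore occur in about 32% of studies of this size, and capnography's in about 9%.

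**6. Overall accuracy.** Each method is correct in 92 of 95 (96.84%; exact lower limit 91.05%). A rule that always answered trachea would be correct in 84/95 = 88.4% while recognising no oesophageal tube. Overall accuracy is therefore dominated by the tracheal tubes.

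**The case against.** The strongest reply is that this is an estimation study. The objectives are to calculate, and the sample size is built on precision, so no null value, power or threshold was required. The intervals are printed in Table 10. The Discussion states the ultrasound specificity interval openly and uses the likelihood-ratio scales of Tables 2 and 3, and the Results soften the claim to fairly accurate. No sentence says that a hypothesis was accepted. Overall accuracy, which Methodology defines, has an exact lower limit above 91%.

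Most of this stands. The missing threshold alone would be a gap in detail, and the estimates and specificity intervals are sound. What does not stand is the step from those intervals to an unqualified verdict. The Discussion treats the ultrasound specificity interval as reassuring because it covers the published 97% to 98%, but the same interval also covers 60%. The likelihood-ratio scales are not tied to the first hypothesis. Ultrasound's positive ratio of 10.74 passes the mark of 10 on a single false positive; two would give 0.976 / (2/11) = 5.4, the moderate band.

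A reader might also go too far the other way and infer a pass mark of 89% (0.94 − 0.05), then say that both methods failed it on specificity and passed it on sensitivity. The documents do not support that:
- The 0.05 is a planned half-width, not a minimum acceptable value.
- With a full 87 oesophageal tubes and a true specificity of 0.94, an exact lower limit of 89% needs at least 84/87, which has probability of only 0.23.
- The 0.94 is for ultrasound specificity. The same reasoning for sensitivity would give 0.98 − 0.05 = 0.93, which both sensitivity lower limits (91.66% and 89.92%) miss.

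**Conclusion.** The concern holds as one about the conclusions, not about the estimates. The data support fairly precise statements on recognising tracheal tubes. For oesophageal tubes they leave specificities down to 58.7% (ultrasound) and 71.5% (capnography) inside the 95% intervals, and no result with 11 tubes could have raised the exact lower limit above 71.5%. The unqualified wording in the Abstract, Discussion and Conclusion exceeds this, and Limitations does not disclose it.

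This rests on the counts in Tables 8 and 9 and on the Clopper-Pearson intervals that the documents name. The Wilson and Jeffreys limits move the perfect-score figure to between 74% and 80% and do not change the conclusion. It does not follow that either method is inaccurate for oesophageal tubes: both point estimates are above 90%, and both intervals include high values. The finding is that accuracy was not established with useful precision. No threshold is needed to reach it.

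**What to change.** Treat the first hypothesis as estimation only, and do not introduce 89% or any other pass mark now that the results are known. Reword the Abstract conclusion, the opening of the Discussion and the Conclusion along these lines:

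> Sensitivity for tracheal tubes was 82/84 for ultrasonography (95% CI 91.7% to 99.7%) and 81/84 for capnography (89.9% to 99.3%). Specificity for oesophageal tubes was 10/11 (58.7% to 99.8%) and 11/11 (71.5% to 100%). With 11 oesophageal tubes, accuracy for recognising oesophageal placement was not established with useful precision.

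Wherever overall accuracy is quoted, add that 84 of the 95 tubes were tracheal. Add to Limitations the 11-tube denominator and the resulting half-width of about 14 points at the planning specificity, against the 5 intended.

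No new data or analysis is needed, because the sensitivity and specificity intervals are already in Table 10. The cost is a narrower headline claim.

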After confirmation of the endotracheal tube position, true and false positives and negatives were determined for both the methods as depicted in table 1.

Sensitivity, specificity, positive predictive value and negative predictive value, likelihood ratios; for both ultrasonography and capnography were calculated using their corresponding formulas.³⁷ The results were extrapolated into confidence intervals using Clopper-Pearson confidence interval.³⁷

Table 1. Designation of true and false positives and negatives.

Capnography		Ultrasonography	
Tracheal outcome	Oesophageal outcome	Tracheal outcome	Oesophageal outcome
True positive (TP): final position in trachea.	True negative (TN): final position in oesophagus.	True positive (TP): final position in trachea.	True negative (TN): final position in oesophagus.
False positive (FP): final position in oesophagus.	False negative (FN): final position in trachea.	False positive (FP): final position in oesophagus.	False negative (FN): final position in trachea.

Sensitivity = TP / (TP+FN).

Specificity = TN / (TN+FP).

Positive predictive value (PPV) = TP / (TP+FP).

Negative predictive value (NPV) = TN / (TN+FN).

Confidence intervals, CI (at 95 % level of confidence): for example for sensitivity

CI = (Sensitivity + 1.96SE, sensitivity – 1.96SE). Where SE is standard error,

SE for sensitivity = square root of [sensitivity (1 – sensitivity)/(TP+FN)]³⁷

Accuracy = $(TP+TN) / (TP+TN+FP+FN)$.

(TP=True Positive, TN=True Negative, FP=False Positive, FN= False Negative)

Likelihood ratio of a positive test: was given by

$$LR_{+} = \frac{\text{sensitivity}}{1 - \text{specificity}}$$

The positive likelihood ratio values corresponded to different probabilities as follows³⁷:

Table 2. Interpretation of positive likelihood ratio.³⁷

Positive likelihood ratio value	Probability
0	Excluded disease.
> 10	Large change in likelihood (or in other words high probability of any individual having a positive result on using the diagnostic test).
5 – 10	Moderate change in likelihood.
2 – 5	Small change in likelihood.
1	No change.

Likelihood ratio of negative test: was given by

$$LR_{-} = \frac{1 - \text{sensitivity}}{\text{specificity}}$$

The negative likelihood ratio values also corresponded to different probabilities as follows³⁷:

Table 3. Interpretation of negative likelihood ratio.³⁷

Negative likelihood ratio value	Probability
infinity	Excluded normality.

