Among the 95 subjects, the mean age was found out to be 44.24 years with standard deviation of ± 16.18 years, and the median age was 47 years. The youngest patient was of 16 years, and the eldest patient was 85 years old. Most patients were in the age group of 41 to 50 years.

Table 5. Demographic profile according to age.

Mean \pm SD (in yrs)	Median (in yrs)	Maximum (in yrs)	Minimum (in yrs)
44.24 \pm 16.18	47	85	16

(n=number, SD= Standard Deviation, yrs = years)

[figure not shown]

Fig. 9. Distribution of the subjects into different age groups.

Among the 95 subjects, there were 51 females (53.68%) and 44 males (46.32%) in this study.

[figure not shown]

Fig. 10. Sex-wise profile of patients in the study.

The majority of patients were Brahmins (40%), followed by Chhetris (22.10%), Newars (14.70%), Magars (7.36%), and others (15.84%); as shown in figure 11. Others include Rai (4), Bhaisnav (1), Chaudhary (1), Muslim communities (2), Lama (2), Gurung (1), Damai (1), Tamang (2), Thakuri (1) and Sherpa (1).

BMI

The mean body mass index (BMI) of the 95 patients was found to be 23.55 ± 3.58 (mean \pm standard deviation); the median BMI was 23.72 and the inter-quartile range [20.68 - 25.92], all values expressed in kg/m^2 . The summary is shown in table 3 and figure 12.

[figure not shown]

Fig. 11. Distribution of patients as per ethnicity in this study.

Table 6. Average body mass index (BMI) of patients.

	Mean \pm SD	Range	Median	IQR
BMI (kg/m^2)	23.55 \pm 3.58	16.33 - 33.88	23.72	[20.68 - 25.92]

(SD = Standard Deviation, Range = Maximum - minimum values; IQR = Interquartile range)

[figure not shown]

Fig. 12. Frequency of patients according to WHO classification of BMI.

ASA Physical Status

There were 46 ASA I patients and 49 ASA II patients in this study. The clinical conditions in patients with ASA II status are listed below in table 4. Table 4 does not account for the presence of multiple clinical conditions in the patients.

[figure not shown]

Fig. 13. ASA Physical status distribution of patients.

Table 7. Clinical conditions in ASA II patients.

	No. of patients	
	MCTVC	TUTH
Valvular heart disease	8	0
Coronary heart disease	14	1
Vascular disease	6	0
Hypertension	14	6
Diabetes Mellitus	4	1
Hypothyroidism	3	3
Hepatitis C positive	0	1
Central nervous system disease	0	8

Analytical Statistics and Data

Out of the total 95 intubations, there were 11 oesophageal intubations. The incidence of oesophageal intubation was 11.57% in this study.

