Ultrasonography

Ultrasound falsely detected one oesophageal intubation as tracheal, and two tracheal intubations as oesophageal.

Table 8. Distribution of positives and negatives for ultrasonography.

Position showed by Ultrasound	Endotracheal tube position confirmation		Total
	Trachea	Oesophagus	
Trachea (n)	TP = 82	FP = 1	83
Oesophagus (n)	FN = 2	TN = 10	12
Total	84	11	n = 95

(n=no. of patients, TP=True Positives, FP=False Positives, FN=False Negatives, TN=True Negatives)

The sensitivity, specificity, positive predictive value and negative predictive value (with their corresponding 95% confidence intervals in round brackets) were calculated to be 97.62% (91.66% - 99.71%), 90.91% (58.72% - 99.77%), 98.80% (92.67% - 99.81%) and 83.33% (55.66% - 95.22%) respectively. The positive likelihood ratio was 10.74, which suggested a large change in the likelihood of positive result. The negative likelihood ratio was 0.03 which also suggested a large change in the likelihood of negative result. The accuracy of ultrasonography in confirming endotracheal tube placement was 96.84% (92.92% - 100%).

[figure not shown]

Fig. 14. Distribution of positives and negatives for ultrasonography.

Capnography

There were three false negative results given by waveform capnography. There was no false positive result.

Table 9. Distribution of positives and negatives for capnography.

Position showed by waveform capnography	Endotracheal tube position confirmation		Total
	Trachea	Oesophagus	
Trachea (n)	TP = 81	FP = 0	81
Oesophagus (n)	FN = 3	TN = 11	14
Total	84	11	n=95

(n=no. of patients, TP=True Positives, FP=False Positives, FN=False Negatives, TN=True Negatives)

[figure not shown]

Fig. 15. Distribution of positives and negatives for capnography.

The sensitivity, specificity, positive predictive value and negative predictive value (with their corresponding 95% confidence intervals in round brackets) of capnography were calculated to be 96.43% (89.92% - 99.26%), 100% (71.51% - 100%), 100% (100% - 100%) and 78.57% (54.69% - 91.76%) respectively. The positive likelihood ratio was infinity. The negative likelihood ratio was 0.04 which suggested a large change in the likelihood of negative result. The accuracy of capnography in confirming endotracheal tube placement was 96.84% (92.92% - 100%).

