This study used both sidestream and mainstream capnographs. This was because of availability of different types of capnograph at the study sites. The details of sampling line delay are discussed later.

Ultrasonography vs Capnography

Both ultrasonography and waveform capnography were found to be good, reliable and fairly accurate diagnostic methods of confirming endotracheal tube position. Though ultrasonography and capnography were equally sensitive and capnography seemed more specific; the sensitivity, specificity, PPV, NPV of ultrasonography were comparable (statistically not different as seen by their confidence intervals) to waveform capnography.

The combination of ultrasonography and capnography increased precision (accuracy) over using either one of them in this study. Since the studies done previously had compared ultrasonography against capnography as the standard and thus calculated the sensitivity, specificity, PPV, NPV of ultrasound; these were not able to show if ultrasound had increased accuracy over using capnography alone.

Both of these methods are now known to be equally reliable. Hence in case of unmatched result given by these two methods in a patient, a third highly reliable method of confirmation has to be used because both ultrasonography and capnography have statistically not different false positive (1 – specificity) and false negative (1 – sensitivity) rates.

There was generally good agreement between the results produced by ultrasonography and capnography as shown by the kappa value of 0.749 with 95% confidence interval of (0.567 – 0.931). Other studies have shown a good or a very good agreement of these two methods by kappa statistics. The kappa value calculated by Adi et al³⁰, Chou et al²⁸, Karacebay et al²⁷ and Chintamani et al³⁴ were 0.85, 0.93 (0.84 – 1.00), 0.85 and 0.76 respectively.

Real-time, transtracheal, transverse suprasternal ultrasonography was significantly faster ($p = 0.011$) than capnography by 16.36 ± 3.23 seconds (mean \pm SD) in confirming endotracheal tube position in this study. The subgroup analysis between mainstream and sidestream capnographs also showed that the type of waveform capnograph device used did not affect the significant difference in time of ultrasound over capnograph in confirming endotracheal tube position.

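### The ±5-point sample size for specificity was counted in patients rather than oesophageal intubations; with 11 such cases, equal reliability on specificity is not shown

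*Combined protocol and SAP*

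**What the plan says.** The Sample size section gives a single-proportion precision formula for a sensitivity or a specificity. It then says which value was entered: a meta-analysis found "the sensitivity and specificity of suprasternal transtracheal ultrasound for endotracheal tube confirmation to be 0.98 and 0.94 respectively, the specificity value for" P being the one taken. The margin d is 5%, z is 1.96, and the result is 86.66. The section ends: "Adjusting for 10% drop outs and defaulters, a sample size of 95 was thus taken". These are patients of any kind, with no step for how many would be intubated in the oesophagus.

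The Operational Definitions make trachea the positive result and oesophagus the negative result, and define "Specificity = TN / (TN+FP"), so only tubes that are truly in the oesophagus enter the denominator. The Results report: "Out of the total 95 intubations, there were 11 oesophageal intubations".

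The Statistical Analysis section plans no comparison of accuracy between the methods and sets no equivalence margin. The Discussion (Ultrasonography vs Capnography) nevertheless calls ultrasonography's accuracy measures "comparable (statistically not different as seen by their confidence intervals) to waveform capnography". It adds "Both of these methods are now known to be equally reliable" and says that the false positive and false negative rates do not differ statistically. The Conclusion repeats the claim of equal reliability. The Limitations list three items, and none concerns the number of oesophageal intubations.

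**The concern.** A precision formula returns the number of subjects in the denominator of the proportion it is used for. For specificity here, those subjects are oesophageal intubations. To turn 86.66 into a number of patients, it has to be divided by the expected proportion of oesophageal intubations, and this was not done. The stated ±5 points is therefore not a property of the design for the parameter it was sized on.

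With trachea as positive, 1 − specificity is the rate at which an oesophageal tube is passed as tracheal, the dangerous error. A statement that two methods are equally reliable on that measure needs data that can exclude an important difference. Two separate, wide intervals that overlap do not do that.

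The source of P also needs checking. The Sample size section credits 0.98 and 0.94 to the meta-analysis in reference 6. The Literature Review reports that meta-analysis as 0.93 and 0.97 for detecting oesophageal intubation, which becomes 0.97 and 0.93 with trachea as positive. It gives 0.98 and 0.94 for the emergency subset of the other meta-analysis, reference 21.

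**Working it through.** **Inputs.** P = 0.94, d = 0.05, z = 1.96 and 10% dropout (Sample size); 11 oesophageal and 84 tracheal intubations, ultrasonography 10/11 and 82/84, capnography 11/11 and 81/84 (Results, Tables 8 and 9).

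**1. The plan's figure.** n = z²P(1−P)/d² = 1.96² × 0.94 × 0.06 / 0.05² = 86.67, and 86.67 × 1.10 = 95.3. The stated 86.66 and 95 are reproduced.

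**2. Precision for specificity with 11 cases.** Same formula: 1.96 × √(0.94 × 0.06 / 11) = 0.140, or ±14 points against ±5 planned.

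Exact (Clopper-Pearson) intervals:
- 10/11: 58.72–99.77%, which is 90.91 − 58.72 = 32 points below the estimate and 99.77 − 90.91 = 9 above.
- 11/11: lower limit 0.025^(1/11) = 71.51%.

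Both match the report; capnography's sensitivity and specificity are printed as "96.43% (89.92% - 99.26%), 100% (71.51% - 100"%). Since a perfect score leaves a lower limit of 71.51%, no result from 11 cases could give an exact interval within ±5 points.

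**3. Oesophageal cases needed for a high exact lower limit with no errors.** For 90%: ln(0.025)/ln(0.90) = 35.01, so 36. For 95%: ln(0.025)/ln(0.95) = 71.9, so 72.

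**4. Patients needed for ±5 by the plan's formula.** This is 86.66 divided by the oesophageal proportion, which the plan does not state. Over the figures in the documents:

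| Proportion oesophageal | Source | Patients, before dropout |
|---|---|---|
| 11/95 = 11.6% | observed | about 750 |
| 16% | upper end, emergency (Discussion) | about 540 |
| 6% | lower end, emergency (Discussion) | about 1,450 |
| 2% | ceiling for elective (Discussion) | about 4,300 |

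At 2%, 95 patients would be expected to give 95 × 0.02 = 1.9 oesophageal cases.

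**5. Sensitivity.** 1.96 × √(0.98 × 0.02 / 84) = 0.030, or ±3 points; the exact interval for 82/84 is 91.66–99.71%. The ±5 target is met by the plan's formula.

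**6. Paired comparison.** Specificity: capnography was right in all 11 and ultrasonography in 10, so 10 cases were right by both and 1 by capnography only.

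Sensitivity: the Results state "The 84 tracheal intubations were correctly identified by both ultrasonography and capnography or either one of these methods", so no tracheal case was missed by both. With 2 ultrasonography and 3 capnography errors this gives 79 right by both, 3 by ultrasonography only, 2 by capnography only and 0 by neither.

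Newcombe paired 95% intervals:
- Specificity, capnography minus ultrasonography: 1/11 = 9.1 points (−17.8 to +37.7). Correlation is set to zero because one margin is empty.
- Sensitivity, ultrasonography minus capnography: 1/84 = 1.2 points (−5.2 to +7.9).

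**7. Check of the pair counts.** They imply 1 + 3 + 2 = 6 disagreements in 95. Chance agreement from the margins is (83 × 81 + 12 × 14)/95² = 0.7635, so kappa = (89/95 − 0.7635)/(1 − 0.7635) = 0.733. The report gives 0.749. With these margins the number of disagreements must be even; 4, 6 or 8 give 0.822, 0.733 or 0.644. No pairing gives 0.749, so the counts and the kappa should both be checked against the data sheet.

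**The case against.** The exact interval for specificity is printed beside the estimate in the Abstract, the Results and the Discussion, and no result claims that ±5 was reached. The Abstract's conclusion says only that both methods are reliable and accurate, and the Discussion concedes that capnography seemed more specific. The timing objectives do not depend on the specificity denominator, and sensitivity is well supported. The citation may not be an error: the values given for reference 6 in the Literature Review pool tracheal and lung ultrasonography, whereas the Sample size section speaks of the suprasternal technique.

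Much of this stands. The intervals are honest, the overclaim lies in particular sentences of the Discussion and Conclusion, and the citation can only be flagged for checking. What does not follow is that the text may stay as it is. The sample-size statement attaches ±5 points to specificity without qualification, the Limitations are silent, and the Discussion and Conclusion infer equality from the intervals that show how little is known about specificity. The choice of incidence affects only how large the shortfall is. The elective figure below 2% would make it larger.

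**Conclusion.** The concern holds. The sample size of 86.66 is a number of oesophageal intubations, it was applied to all patients, and 11 were obtained. Precision for specificity is ±14 points by the plan's formula, and 58.72–99.77% by the exact interval for ultrasonography, against ±5 intended. Equal reliability is unsupported for specificity, where a difference of up to 37.7 points in favour of capnography is not excluded. Equality wording that rests on sensitivity and overall accuracy has better support, but no margin was set for those either.

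The specificity pair counts follow directly from Tables 8 and 9. The sensitivity pair counts rest on the statement that every tracheal intubation was identified by at least one method, and they do not reproduce the reported kappa. The total of about 750 patients assumes the observed incidence.

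**What to change.** 1. **Sample size.** State that 86.66 is the number of oesophageal intubations needed for ±5 points on specificity, that it was not inflated for their incidence, and that 95 patients do not deliver that precision. Do not rebuild the a priori calculation from the observed 84 and 11.
2. **Limitations.** Add: Specificity was estimated from 11 oesophageal intubations; for ultrasonography the exact 95% CI was 58.72–99.77%, so the planned ±5 points was not reached.
3. **Discussion and Conclusion.** Replace the equal-reliability wording, and the inference from separate intervals, with the paired differences and 95% intervals for sensitivity and specificity, with pair counts taken from the data sheet. Conclude that no difference was detected and that specificity is imprecise (11 oesophageal intubations).
4. **Source of P.** Reconcile the citation for 0.98 and 0.94 between the Sample size section and the Literature Review, and say which result counts as positive. If 0.93 were the right value, the formula would give 1.96² × 0.93 × 0.07 / 0.05² = 100.

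The cost is wording in four sections and two intervals from existing data. No patients are added, and no reported accuracy estimate or interval changes. The study has to state that its precision for specificity fell short and give up the claim of equal reliability. Retrieving the pair counts may also show that the reported kappa needs correcting.
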